10.6 Randomization and Treatment Assignment

At the end of the run-in period, subjects are randomized to either the HCL or the Control arm. Depending on the type of therapy subjects are using at the start of the study the randomization will be to participate in the Hybrid Closed Loop arm or use their own therapy for the duration of the study period. Randomization is generated via the RDC study database.

Note: Subjects 2-6 years of age will automatically enter the HCL arm at the end of the run-in period.

CEP304 Clinical I				
CEP304DOC	Revision	Н	Page 102 of 182	Medtronic

10.7 Assessment of Safety

10.7.1 Adverse Event

The Medtronic Clinical Research Department, in conjunction with the Regulatory Affairs Department, will monitor and manage adverse event reporting for the study and determine whether the event requires reporting to regulatory agencies. The sponsor will ensure timely Adverse Event reporting to meet regulatory requirements.

Throughout the course of the study, investigational centers will make all efforts to remain alert to possible reportable adverse events or untoward findings. The study personnel will elicit reports of adverse events from the subject at each visit (including phone calls) documenting the medical diagnosis, date of event start and end, causality (relationship to device or procedure), treatment, resolution and description that includes the details of the event.

10.7.2 Causality Assessment

An adverse event is not automatically related to the study device or procedure simply because the subject is wearing the device and participating in the study. The event should be reviewed to determine if the device or study procedure could have possibly caused the event and therefore is related to the study device or procedure. It should also be noted that should the control arm utilize a non-Medtronic device, these would not be considered device related.

Causality assessment is the determination of the relationship between an adverse event and the device being studied. It is expected that the investigational center will review all elements surrounding the adverse event to properly assess the causality of the event to the study device or to a study procedure.

This review would include the subjects description of the event, study device uploads and medical records (if applicable) from the treating facility. These records will be made available to sponsor.

Investigators should classify the relationship between the AE and the study device or study procedures using one of the five possible causality categories listed below:

- Not related: relationship to the device or procedures can be excluded when:
 - the event is not a known side effect of the product category the device belongs to or of similar devices and procedures
 - the event has no temporal relationship with the use of the investigational device or the procedures;

CEP304 Clinical I	investigatio	n Pla	an	
CEP304DOC	Revision	Н	Page 103 of 182	Medtronic

- the event does not follow a known response pattern to the medical device (if the response pattern is previously known) and is biologically implausible;
- the discontinuation of medical device application or the reduction of the level of activation/exposure - when clinically feasible – and reintroduction of its use (or increase of the level of activation/exposure), do not impact on the serious event;
- the event involves a body-site or an organ not expected to be affected by the device or procedure;
- the event can be attributed to another cause (e.g. an underlying or concurrent illness/ clinical condition, an effect of another device, drug, treatment or other risk factors);
- the event does not depend on a false result given by the investigational device used for diagnosis, when applicable;
- o harms to the subject are not clearly due to use error;
- o In order to establish the non-relatedness, not all the criteria listed above might be met at the same time, depending on the type of device/procedures and the serious event.
- Unlikely: the relationship with the use of the device seems not relevant and/or the event can be reasonably explained by another cause, but a relationship to the device cannot be completely ruled out.
- Possible: the relationship with the use of the investigational device is weak. Alternative causes are also
 possible (e.g. an underlying or concurrent illness/ clinical condition or/and an effect of another device,
 drug or treatment). Cases where relatedness cannot be assessed should also be classified as possible.
- Probable: the relationship with the use of the investigational device seems relevant and/or the event cannot reasonably be explained by another cause.
- Causal relationship: the event is associated with the investigational device or with procedures beyond reasonable doubt when:
 - the event is a known side effect of the product category the device belongs to or of similar devices and procedures;
 - the event has a temporal relationship with investigational device use/application or procedures;

CEP304 Clinical				
CEP304DOC	Revision	Н	Page 104 of 182	Medtronic

- the event involves a body-site or organ that
 - the investigational device or procedures are applied to;
 - the investigational device or procedures have an effect on;
- o the event follows a known response pattern to the medical device (if the response pattern is previously known);
- o the discontinuation of medical device application (or reduction of the level of activation/exposure) and reintroduction of its use (or increase of the level of activation/exposure), impact on the event (when clinically feasible);
- o other possible causes (e.g. an underlying or concurrent illness/ clinical condition or/and an effect of another device, drug or treatment) have been adequately ruled out;
- harm to the subject is due to error in use;
- the event depends on a false result given by the investigational device used for diagnosis, when applicable;
- o In order to establish the relatedness, not all the criteria listed above might be met at the same time, depending on the type of device/procedures and the serious event.

Example: A severe hyperglycemia adverse event with the following event description would have the following causality assessment for device relatedness:				
Improved glucose without an infusion set/site change	Not related			
Changed infusion set with glucose improvement	Possible			
Infusion set fell out, bent cannula, occlusion alarm	Causal relationship			

10.7.3 **Anticipated or Unanticipated**

If the adverse event is determined to be related to the study device the sponsor will then assess the event to determine if it is anticipated or unanticipated.

Anticipated: the event is identified in the CIP; labeling; report of priors/IB or user guide.

CEP304 Clinical I				
CEP304DOC	Revision	Н	Page 105 of 182	Medtronic

Unanticipated: the event has not been previously identified in the CIP; labeling; report of priors/IB,
 Investigator brochure, or user guide

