 - Patient administering boluses by entering false carb doses leading to hypoglycemia or hyperglycemia
 - Patient entering false glucose values for any reason leading to hypo and hyperglycemia
 - Patient entering false
 BG values for
 calibration leading to
 hypo or hyperglycemia
- Sensor failure resulting from patient failure to calibrate leading to hypo or

Mitigation

Mitigations specific to the HCL System:

- Investigational center staff and subjects will be instructed to follow the provided user guides for insulin pump management.
- Subjects will be trained prior to study device use and diabetes management principles and told to call with problems.
- Subjects will be required to check SMBG 4-6 times a day and also before driving (as applicable).
- Subjects will be told to have glucose on hand for hypoglycemia
- Subjects will be asked to avoid the use of products containing Acetaminophen
- If acetaminophen is taken, subjects will be instructed to use additional BG meter readings (they are not to calibrate with those readings) to verify their glucose levels.
- Subjects will be instructed to exit AutoMode

CEP304 Clinical				
CEP304DOC	Revision	Н	Page 121 of 182	Medtronic

hyperglycemia Sensor over-reading resulting in hypoglycemia Sensor under-reading resulting in hyperglycemia Sensor missed transmission, or any other fault resulting in no SG value, leading to hyper or hypoglycemia Voluntary insulin delivery (with the pump or with a syringe) immediately prior to entering HCL may result in severe hypoglycemia despite shutting down insulin delivery by the algorithm Patient takes insulin via injection while in Closed

- Loop
- Hypoglycemia or hyperglycemia related to entering or exciting closed loop
- Insulin over-delivery due to Acetaminophen

CEP304 Clinical I				
CEP304DOC	Revision	Н	Page 122 of 182	Medtronic

Risks associated with
hyperglycemia include

- DKA
- Symptomatic ketosis
- Cardiovascular event
- Dehydration
- Potassium and sodium imbalance
- Shock
- Altered mental status
- Coma
- Acidosis

Prevention and mitigation hyperglycemic risks include:

- Investigational center staff and subjects will be instructed to follow the provided user guides for insulin pump management.
- Subjects and/or parent guardian will be trained on study device and diabetes management principles.
- Subjects will be trained prior to study device use and diabetes management principles.

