Third: Based on their meetings, DMC will recommend a decision to the sponsor regarding the following:

- Whether or not enrollment should be halted.
- Whether or not the entire study will need to be stopped including for those subjects who have received study devices already.

Fourth: During Interim analysis, independent statistician will perform sample size re-estimation and report it to DMC. DMC will then provide a recommendation:

- Whether or not N of enrollment per Group should be increased
- Whether or not the entire study will need to be stopped for futility

General guidance for DMC's recommendations to sponsor should be based on the following:

In general, a DMC recommendation regarding study stoppage or resumption of enrollment should be made to the sponsor within 1 week of the DMC meeting where the determination is made. However, if more data is needed, the DMC may meet again to re-assess their decision within 2 weeks or when required data becomes available.

Review of events may require the following information. Final disposition may be delayed based on obtaining this information:

- Monitoring by sponsor at site
- Device return and failure analysis
- CareLink upload and review of CareLink reports
- Subject clarification to site regarding details about the event
- Source documents that support event: Paramedic records; ER records; Lab records; Hospital admission and discharge summary

The following factors should be carefully considered in the DMC's recommendation to sponsor:

- 1. Was the severe hypoglycemia or DKA related to the HCL algorithm, or was it related to a known insulin pump risk? For example, a question that may be considered in DKA would be whether the event was related to an infusion set issue or caused by the HCL algorithm.
- 2. Another important consideration would be if the severe hypoglycemia, severe hyperglycemia or DKA event was related to a device malfunction versus patient non-compliance. For example, if a software anomaly leading to an under-delivery of insulin is discovered versus the subject repeatedly ignoring alarms prompting the subject to take action.

CEP304 Clinical				
CEP304DOC	Revision	Н	Page 133 of 182	Medtronic

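### The worked example in Protocol 10.7.2 rates severe hyperglycemia by the infusion set alone, and can lead sites to rate sensor-, transmitter- or algorithm-caused events Not related

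*Protocol*

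**What the plan says.** Protocol 10.7.2 defines five causality categories and then gives one worked example, introduced as "Example: A severe hyperglycemia adverse event with the following event description would have the following causality assessment for device relatedness". The example has three rows:

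- The first gives the rating Not related to an event described as "Improved glucose without an infusion set/site change".
- The second gives the rating Possible when the set was replaced and glucose then improved.
- The third gives the highest rating, Causal relationship, to faults at the delivery site, listed as "Infusion set fell out, bent cannula, occlusion alarm".

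The definitions before the table are broader. The site is to look at everything bearing on the event, including device uploads. Not related is for events where a relationship can be excluded. If a relationship cannot be fully ruled out, the category is Unlikely. The text under Possible adds: "Cases where relatedness cannot be assessed should also be classified as possible".

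Section 17.1 states that device means any device used in the study and that the causality definitions apply to all events. Section 16.1 names "Sensor under-reading resulting in hyperglycemia" as an HCL risk, together with missed sensor transmission leading to high or low glucose.

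**The concern.** This is a trial of a closed-loop system, and the example given to sites for its hyperglycemic events contains no closed-loop cause. All three rows turn on the infusion set, a component shared with ordinary pump therapy. Improvement without a set change is evidence against a set fault. It says nothing about whether the sensor misread, the transmitter dropped out or the algorithm under-delivered.

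If sites follow the first row as written, known infusion-set events stay in the device-related count, while events specific to the system under test can leave it. Section 18.2 has the DMC track the rate of device-related adverse events. It also has the DMC consider, with DKA as the example, "whether the event was related to an infusion set issue or caused by the HCL algorithm", and a later item there draws a similar contrast that mentions severe hyperglycemia. Site ratings made under the example would inform only the infusion-set side of that question.

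**Working it through.** The point is qualitative and the plan states no figure to reproduce. The check sets the first row beside the other provisions.

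1. **Can a device cause exist without a set fault?** Yes. Under 7.4 and 7.5, Auto Mode calculates insulin from sensor glucose. A sensor that reads low, or a lost signal, can lead to high glucose with an intact set, and 16.1 lists both mechanisms. Neither needs a set change in order to resolve.

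2. **What do the definitions give for such an event?** Dependence on a false result from a diagnostic device is, where applicable, a criterion for Causal relationship, and its absence is a criterion for Not related. If the cause cannot be judged, the rating is Possible. If a relationship is improbable but not ruled out, it is Unlikely. None of these leads to Not related merely because the set was left in place.

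3. **What does the first row give?** Not related, with no condition on the upload, the sensor trace or Auto Mode status. On a literal reading, it and the definitions give different answers for the same event. An algorithm-caused event in which the set also happened to be changed would be Possible under the second row, so the conflict is confined to the first.

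4. **Where does the rating go next?**
   - Device-related event rate (18.2): depends on the rating.
   - Anticipated or unanticipated assessment (10.7.3): made only if the event is rated related.
   - Expedited reporting of severe hyperglycemia (17.2): requires an event that is device related, unanticipated and meets SAE criteria.
   - Total severe hyperglycemia rate (18.2) and per-arm summary (Protocol 5.2.3, SAP 7.10): not conditioned on relatedness.
   - Primary safety endpoint (Protocol 19.1.2, SAP 7.9): severe hypoglycemia and DKA rates, not stated to depend on relatedness.

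5. **How many events?** Only an exposure figure is possible. Table 16 gives a reference rate of 71.64 severe hyperglycemia events per 100 patient-years under age 15, and the minimum for ages 2-6 is 120 subjects, all assigned to HCL. Assuming one year of follow-up each at that rate, 120 × 71.64 / 100 = 86 events. If 20% to 50% resolved without a set change (an assumption; the documents give no share), 0.20 × 86 = 17 to 0.50 × 86 = 43 events would fall under the first row. An unknown part of these would have a sensor, transmitter or algorithm cause.

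**The case against.** The strongest reply is that the table is an illustration. It is labelled as an example, and the text before it requires a full review that includes device uploads. A site that saw a sensor fault on the upload and applied the definitions would not rate the event Not related. This stands. A reader might infer that every severe hyperglycemia event improving without a set change is unrelated by rule, whatever the upload shows; the documents do not say that.

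A reader might also infer that the row breaches the first Not related criterion, "the event is not a known side effect of the product category the device belongs to or of similar devices and procedures", since hyperglycemia is a listed risk. That does not follow, because 10.7.2 says the criteria need not all be met together.

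On consequences, a reader might infer that expedited reporting is widely suppressed. Under 10.7.3 an event identified in the CIP is anticipated, and the sensor mechanisms above are identified in 16.1. They would normally be anticipated even if rated related, so most of that harm falls away. Nor is the DMC blind. It sees all severe hyperglycemia and all SAEs, may call for CareLink reports and failure analysis, and 18.2 refers to a final determination of HCL causality made by the DMC itself.

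Under 18.1 the CEC reviews every severe hyperglycemia report, may disagree with the site and gives its own three-level rating. Nothing binds it to the example. However, 18.1 states no separate rule for such events and does not say whose rating governs the device-related rate.

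Finally, the 17 to 43 events might be read as misclassifications. They are events exposed to the row, and those with a non-device cause may be correctly rated Not related.

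After all this, the unqualified first row remains, together with the absence of any sensor, transmitter or algorithm row.

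**Conclusion.** The concern holds as an internal inconsistency in the guidance sites use to rate relatedness. The example ties device-relatedness of severe hyperglycemia solely to the infusion set. Its first row can lead sites to a rating that conflicts with the definitions in 10.7.2, the scope of device in 17.1 and the HCL risk list in 16.1.

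The effect is possible under-counting of device-related events reported to the DMC, in the direction that favours the closed-loop components. Its size cannot be derived: the documents give neither the share of events resolving without a set change nor the share caused by the sensor, transmitter or algorithm. The conclusion assumes that at least some sites apply the row as written and that not every such rating is corrected on CEC review.

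**What to change.** Reconcile the example in Protocol 10.7.2 with the definitions that precede it:

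- State that the first row applies only when review of the upload shows no sensor, transmitter, pump or algorithm contribution. Otherwise the five category definitions govern, with Possible when relatedness cannot be assessed.
- Add a row for hyperglycemia in which the upload points to a sensor or algorithm cause.
- Have the CEC, within its existing review of all severe hyperglycemia, confirm events coded Not related on the basis of the first row.

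The cost is an amendment to one table and a check of uploads already collected. The downside is a somewhat higher reported device-related rate.

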10.8 Recording Data

In the Oracle Clinical Remote Data Capture (OC-RDC) database, the investigational centers will be identified numerically, i.e. from 001 to 070 (depending on center number). At the Screening visit, investigational center staff will assign each subject a sequential ID number that corresponds to a pre-defined casebook in the OC-RDC database.

Each case book will contain all relevant Case Report Forms for each subject. Each subject will be assigned a unique identifier All study documents, electronic Case Report Forms (eCRFs) and correspondence will use this identifier sequence in lieu of a subject's name or initials.

10.9 Deviation Handling

A deviation is any instance(s) of failure to follow, intentionally or unintentionally, the requirements of the protocol. It is expected that the investigator will conduct this clinical trial in compliance with the protocol and all applicable regulations governing the conduct of clinical research involving human subjects. Failure to do so could result in one or all of the following:

- Observation in the monitoring report
- Deviation to document the event
- Corrective action plan
- Investigational center disqualification
- Notification to the regulatory authorities / IRB/EC depending on the severity of the deviation and reporting requirements

The investigator is responsible for protecting the safety and welfare of the clinical research subjects.

Reporting of Deviations

USA (to Sponsor and IRB): Any deviation from the CIP shall be recorded in eCRF together with an explanation for the deviation. Notice of deviations from the CIP to protect the life or physical well-being of a subject in an

CEP304 Clinical 1				
CEP304DOC	Revision	Н	Page 106 of 182	Medtronic

emergency shall be given as soon as possible, but no later than 5 working days after the emergency occurred. (21 CFR 812.150(a)(4))

Europe (Sponsor, Ethics Committee and Regulatory Authority): Any deviation from the CIP shall be recorded in eCRF together with an explanation for the deviation. Deviations shall be reported to the sponsor who is responsible for analyzing them and assessing their significance.

Note: When relevant, ECs, regulatory authorities or the appropriate regulatory bodies should be informed. (ISO 14155:2011)

Notice of deviations from the CIP to protect the life or physical well-being of a subject in an emergency shall be given as soon as possible, but no later than 5 working days after the emergency occurred.

No waivers for deviations from CIP will be allowed.

Canada, Australia and New Zealand (Sponsor and Ethics Committee): Any deviation from the CIP shall be recorded in eCRF together with an explanation for the deviation. Notice of deviations from the CIP to protect the life or physical well-being of a subject in an emergency shall be given as soon as possible, but no later than 5 working days after the emergency occurred.

10.10 Subject Exit, Withdrawal or Discontinuation

Subjects may choose to withdraw from the study at any time by notifying investigational center staff of their intent.

If a subject chooses to end his or her study participation or if a subject is removed from the study at the Investigator's discretion, the reason for termination must be documented both in source documents and on the appropriate eCRF. All study devices and supplies must be returned and the return documented both in source documents and on the appropriate eCRF.

Subjects may also be withdrawn from the study at the discretion of the Investigator. A subject will be withdrawn from the study if:

- In the opinion of the Investigator, the subject's health or safety would be compromised by continuing in the study
- In the opinion of the Investigator, it is in the subject's best interest to discontinue participation in the study
- During the course of the study, subject begins participation in another investigational study (drug or device).

CEP304 Clinical Investigation Plan				
CEP304DOC	Revision	Н	Page 107 of 182	Medtronic

- During the study it becomes known that subjects are using own SMBG or system that replaces SMBG
- During the course of the study, subject begins abusing illicit drugs or marijuana.
- During the course of the study subject begins abusing prescription drugs.
- During the course of the study subject begins abusing alcohol.
- During the course of the study subject begins using pramlintide (Symlin), DPP-4 inhibitors, liraglutide (Victoza or other GLP-1 agonists), metformin, canagliflozin (Invokana or other SGLT2 inhibitors).
- During the course of the study, subject begins using hydroxyurea.
- During the course of the study, subject receives red blood cell transfusion or erythropoietin.
- During the course of the study, the subject demonstrates that he/she is not able to comprehend instructions for study procedures, as evaluated by the appropriate research staff.
- During the study, subject repeatedly activates SmartGuard when instructed otherwise (e.g. Auto Mode is turned on in SAP Cohort)
- During the course of the study, subject is taking oral, injectable, or IV glucocorticoids for 3 or more weeks (e.g. oral prednisone daily or weekly glucocorticoid administration)
- During the study, (female) subject becomes pregnant.
- During the study, the subject experiences two severe hypoglycemic episodes
- The first episode of Severe Hypoglycemia may lead to withdrawal, if it is secondary to subject noncompliance or other individual safety concerns:
 - Subject is not using the bolus wizard
 - Subject is not checking blood glucose using finger sticks
 - Subject is non-compliant with sensor wear
 - Subject is not following protocol procedures
- During the study, the subject experiences one episode of DKA
- During the study subject has a cardiovascular event or any vascular event such as stroke.

Documentation of the reason(s) leading to subject withdrawal will be kept in the subject's source file.

CEP304 Clinical I				
CEP304DOC	Revision	Н	Page 108 of 182	Medtronic

For Europe only: If patient withdrawal is due to problems related to the device safety or performance, the investigator shall ask for the subject's permission to follow his/her status/condition outside the clinical investigation.

Lost to Follow-up:

Lost to Follow-up refers to a subject who was actively participating in the study, but is no longer keeping study visit appointments and/or fails to respond to communications from the investigative site. A subject is only considered to be lost to follow-up in the event the investigational center is unable to determine the status of the subject. It is recommended that the Investigative site:

- Document at least 2 separate attempts to contact subject by phone
- If no response to phone contact, send the subject a registered letter with return receipt
- Requesting the subject contact the investigational center
- If there is no response, the subject should be considered lost to follow-up and investigative site would withdraw the subject

If the subject contacts the investigational center and wishes to withdraw, the subject would no longer be lost to follow-up but instead would be documented as subject withdrawing consent to continue in the study.

10.11 **Investigational Center Disqualification**

Medtronic and/or the IRB/EC retain the right to disqualify an investigational center and remove all study materials at any time. Specific instances, which may precipitate investigational center disqualification, include but are not limited to:

- Unsatisfactory subject enrollment with regard to quality and quantity.
- Persistent non-compliance to protocol procedures on the part of an Investigator/investigational center. Inaccurate, incomplete, and/or untimely data recording on a recurrent basis.
- The incidence and/or severity of adverse experiences in this or other studies indicating a potential health hazard caused by the device.
- Unsatisfactory accountability of devices.

CEP304 Clinical I				
CEP304DOC	Revision	Н	Page 109 of 182	Medtronic

A written statement fully documenting the reasons for such a termination will be provided to Medtronic, the Institutional Review Board (IRB) or Ethics Committee (EC) and other regulatory authorities, as required.

11. Stopping Rules

